11.1.2. Exact confidence intervals (CIs)

The exact confidence interval within a group for an incidence rate (per 100 person-years):

To estimate the confidence limit of the incidence rate, the exact Poisson confidence limit will be used [Clopper, 1990]:

If *n* is the number of subjects presenting a given characteristic among these *Ny* subjects per year, the true incidence rate can be estimated by (n/Ny)*100. Its exact (1 -)% confidence interval is obtained from:

CINV(/2, 2*n)/2/Ny*100 as the lower boundary

and

CINV((1- /2),2(n+1))/2/Ny*100* as the upper boundary.

where *CINV(probability, degrees of freedom)* returns the inverse of the chi-squared probability distribution and is the type I error rate.

11.1.3. Computation of proportion affected

Proportion affected will be computed as the number of subject who had at least one episode in the age interval divided by the total number of subjects at start of the age interval. A 95% CI will be computed using an exact method for a Poisson variable.

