simulation (Number of clusters; Overall number of children- years; incidence)	Number of children-years by cluster (P5; Median; P95)	Proportion of cases by cluster (P5; Median; P95)	DE : Design Effect (P5; Median; P95)	ρ : intra-cluster correlation (P5; Median; P95)	
9; 2400; 0.03	136; 266; 401	0; 0.028; 0.086	2.51; 6.46; 13.67	0.006; 0.021; 0.047	
12; 2400; 0.03	100; 201; 300	0; 0.027; 0.087	2.57; 5.13; 9.49	0.008; 0.021; 0.042	
15; 2400; 0.03	81; 160; 239	0; 0.027; 0.088	2.29; 4.34; 7.74	0.008; 0.021; 0.042	
18; 2400; 0.03	68; 133; 199	0; 0.026; 0.091	2.08; 3.89; 6.69	0.009; 0.022; 0.043	

P = Percentile

Few active studies reported the overall RSV-associated LRTI incidence rates (with or without hospitalization). According to the results observed in a birth cohort conducted in Kenya [Nokes, 2008] we expect that the RSV-associated LRTI rate will be 8 times greater than the hospitalization rate.

As the subjects may dropout from the study due to a variety of reasons, e.g. migration from the study area, the sample size has been increased to accommodate the same. Assuming a drop-out rate of about 20% during the course of follow-up approximately 400 subjects by country/region and 2400 subjects overall will need to be recruited.

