6.6. Incidence analysis

6.6.1. Analysis of co-primary objectives: incidence of RSV respiratory disease

For this objective, the analysis will be based on PPS.

For clarity the analysis of RSV disease incidence is summarised in the table below showing endpoints and analytic methods.

200150 (EPI-RSV-005 BOD)

Statistical Analysis Plan Amendment 1 Final

For each of the following endpoints you could find the case definitions in Table 4:

- RSV RTI with suspicion of involvement of LRT
- WHO RSV LRTI
- WHO RSV LRTI hospitalisation
- WHO RSV severe LRTI
- WHO RSV severe LRTI hospitalisation
- WHO RSV hospitalisation

Table 12Summary of RSV incidence analyses for primary objectives

Endpoints	Incidence analysis method	Subgroup
RSV RTI with suspicion of involvement of LRT WHO RSV LRTI WHO RSV severe LRTI RSV hospitalisation WHO RSV LRTI hospitalisation WHO RSV severe LRTI hospitalisation	Incidence rates of first episode Cumulative probability of first episode (Kaplan Meier)	Overall, by country, by age intervals, by transmission interval
RSV RTI with suspicion of involvement of LRT WHO RSV LRTI WHO RSV severe LRTI RSV hospitalisation WHO RSV LRTI hospitalisation WHO RSV severe LRTI hospitalisation	Proportion affected by all new episodes	Overall and by country, by age intervals
RSV RTI with suspicion of involvement of LRT WHO RSV LRTI WHO RSV severe LRTI RSV hospitalisation WHO RSV LRTI hospitalisation WHO RSV severe LRTI hospitalisation	Incidence proportion of first episode	Overall and by country, by monthly age

For each endpoints listed in the previous table the 95% CI will be computed as described in section 11.1.2 depending on the age category considered and the method listed in the analysis column. Kaplan-Meier curves presenting the cumulative probability of first episode will be displayed overall and by country. The cumulative probability of presenting first episode will be given with its 95% CI at the end of the follow-up.

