
Center	Total N =	
	n	%

N = number of subjects of total enrolled cohort

n = number of subjects enrolled for a given center

Center = GSK biologicals assigned center number

% = n/N

- 12.3. Incidence
- 12.3.1. Primary incidence analysis
- 12.3.1.1. (PO1) To determine the total health burden* of RSV-associated RTI with a suspicion of involvement of the lower respiratory tract
- Template 7 Incidence rate of first episode of [RSV RTI with suspicion of involvement of LRT, WHO RSV LRTI, WHO RSV severe LRTI, RSV hospitalization, WHO RSV LRTI hospitalization, WHO RSV severe LRTI hospitalization], by age interval overall and by country (PPS)

						95% exact Cl	
Country	Age interval (Months)	Total number of subjects	Total number of first episode	Total number of person- years	Incidence rate (100 person- years)	LL	UL
Overall	0-5						
	6-11						
	0-11						
	12-23						
	0-23						
<each country=""></each>							1

Incidence rate computed using the number of first episode as numerator and the total number of person-years over the entire follow-up as denominator

CI=confidence interval, LL, UL for incidence = Exact 95% Lower and Upper confidence limits

Template 8 Incidence rate of first episode of WHO RSV LRTI, WHO RSV severe LRTI, RSV hospitalization, by age interval – by country (PPS)

		95% exact CI						
Country	Age interval	Episodes	Total number of subjects	Total number of first episode	Total number of person- years	Incidence rate (100 person- years)	LL	UL
<each country ></each 	0-11 months	WHO RSV LRTI						
		WHO RSV severe LRTI						
		RSV hospitalization						
	12-23 months	WHO RSV LRTI						
		WHO RSV severe LRTI						
		RSV hospitalization						

Incidence rate computed using the number of first episode as numerator and the total number of person-years over the entire follow-up as denominator

CI=confidence interval, LL, UL for incidence = Exact 95% Lower and Upper confidence limits
Statistical Analysis Plan Amendment 1 Final

Template 9 Proportion affected by at least one episode of [RSV RTI with suspicion of involvement of LRT, WHO RSV LRTI, WHO RSV severe LRTI, RSV hospitalization, WHO RSV LRTI hospitalization, WHO RSV severe LRTI hospitalization] by age interval – overall and by country (PPS)

					95% e	xact Cl
Country	Age interval (Months)	Total number of subjects at birth	Total number of subjects affected	Proportion affected	LL	UL
Overall	0-5					
	6-11					
	0-11					
	12-23					
	0-23					
<each country=""></each>						

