Proportion affected computed using the number of subjects experiencing at least one episode as numerator and the total number of subjects at start of the age interval as denominator.

CI=confidence interval, LL, UL for proportion affected = Exact 95% Lower and Upper confidence limits

Template 10 Proportion affected by at least one episode of WHO RSV LRTI, WHO RSV severe LRTI, RSV hospitalization, by age interval – overall and by country (PPS)

						95% e	exact CI
Country	Age interval (Months)	Episodes	Total number of subjects at birth	Total number of subjects affected	Proportion affected	LL	UL
<each country ></each 	0-11	WHO RSV LRTI					
,		WHO RSV severe LRTI					
		RSV hospitalization					
	12-23	WHO RSV LRTI					
		WHO RSV severe LRTI					
		RSV hospitalization					

Proportion affected computed using the number of subjects experiencing at least one episode as numerator and the total number of subjects at start of the age interval as denominator.

CI=confidence interval, LL, UL for proportion affected = Exact 95% Lower and Upper confidence limits

200150 (EPI-RSV-005 BOD)

Statistical Analysis Plan Amendment 1 Final

Template 11 Incidence proportion of first episode of [RSV RTI with suspicion of involvement of LRT, WHO RSV LRTI, WHO RSV severe LRTI, RSV hospitalization, WHO RSV LRTI hospitalization, WHO RSV severe LRTI hospitalization] by monthly age interval in first six month of life– by country (PPS)

					95% exa	act Cl
Country	Age interval (Months)	Total number of subjects at risk	Total number Of first episode	Incidence proportion	LL	UL
<each country=""></each>	Less than 1					
	1					
	2					
	3					
	4					
	5					

Incidence proportion computed using the number of first episode as numerator and the total number of subjects at risk as denominator.

Note that subjects who have presented a first episode in a previous category are not considered in the subsequent age categories.

CI=confidence interval, LL, UL for incidence proportion = Exact 95% Lower and Upper confidence limits

Template 12 Incidence rate of first episode of [WHO RSV LRTI, WHO RSV severe LRTI and RSV hospitalization] in first 6 months of life with <=3 months or >3 months follow up in the transmission season – by country (PPS)

						95%	exact CI
Country	Follow up in transmission season	Total number of subjects	Total number of first episode	Total number of person- years	Incidence rate (100 person- years)	LL	UL

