n= Number of RSV hospitalization episodes meeting the case definitions (an episode is assigned to a single category based on the highest severity of the symptom experienced).

SD=Standard Deviation

Q1 and Q3 = 1st and 3rd quartiles

Min/Max = Minimum/Maximum

Total RSV viral load computed as RSV A Viral load + RSV B Viral load

Note:

There may have been multiple swabs for an episode. In such cases, the swab with highest viral load was considered for this analysis

Template 33 Descriptive statistics of *total* RSV viral load during all *RSV* hospitalization episodes classified according to WHO severity scale occurring during the [first year of life - second year of life- 2 year follow-up period] by overlapping disease severity (PPS)

Category	n	Mean	95%	SD	Q1	Median	Q3	Min/Max
			CI					
RSV hospitalization								
WHO RSV LRTI hospitalization								
WHO RSV Severe LRTI hospitalization								

n= Number of RSV hospitalization episodes meeting the case definitions

SD=Standard Deviation

Q1 and Q3 = 1st and 3rd quartiles

Min/Max = Minimum/Maximum

Total RSV viral load computed as RSV A Viral load + RSV B Viral load

Note:

200150 (EPI-RSV-005 BOD) Statistical Analysis Plan Amendment 1 Final

Template 34 Incidence rate of first episode of [RSV LRTI (exploratory), RSV severe LRTI (exploratory)], by age interval – overall and by country (PPS)

						95% (exact CI
Country	Age interval (Months)	Total number of subjects	Total number of first episode	Total number of person- years	Incidence rate (100 person- years)	LL	UL
Overall	0-5						
	6-11						
	0-11						
	12-23						
	0-23						
<each country=""></each>							

Incidence rate computed using the number of first episode as numerator and the total number of person-years over the entire follow-up as denominator

CI=confidence interval, LL, UL for incidence = Exact 95% Lower and Upper confidence limits

Template 35 Proportion affected by at least one episode of [RSV LRTI (exploratory), RSV severe LRTI (exploratory)] by age interval – overall and by country (PPS)

					95% e	xact Cl
Country	Age interval (Months)	Total number of subjects at birth	Total number of subjects affected	Proportion affected	LL	UL
Overall	0-5					
	6-11					
	0-11					
	12-23					
	0-23					
<each country=""></each>						

Proportion affected computed using the number of subjects experiencing at least one episode as numerator and the total number of subjects at birth as denominator.

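### The SAP gives two denominators for proportion affected; the at-birth one would understate the 6-11 and 12-23 month rows by about 8% and 15% relative

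*SAP*

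**What the plan says.** SAP 6.6.1, Table 12, lists "Proportion affected by all new episodes" among the incidence summaries for the first co-primary objective. It covers six RSV endpoints, overall, by country and by age interval. The denominator is described in these places:

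- **SAP 11.1.3 (method):** children with at least one episode, "divided by the total number of subjects at start of the age interval". It does not say whether this means children still being followed at that age.
- **Template 9 (SAP 12.3.1.1), column heading:** "Total number of subjects at birth". Its rows are 0-5, 6-11, 0-11, 12-23 and 0-23 months. Template 10 has the same heading, with rows for 0-11 and 12-23 months.
- **Templates 9 and 10, footnotes:** "the total number of subjects at start of the age interval as denominator".
- **Template 35 (SAP 12.5.2.1, exploratory case definitions):** at birth in the heading and again in the footnote, "the total number of subjects at birth as denominator".

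The per-protocol set (SAP 5.1.3) keeps children who drop out, up to their censoring. Protocol 8.2 does not replace withdrawals. Protocol 9.3 sizes the study "Assuming a drop-out rate of about 20% during the course of follow-up".

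**The concern.** A programmer who follows the headings and one who follows the footnotes would produce different numbers for the 6-11 and 12-23 month rows. With the at-birth denominator, a child who left at 5 months counts as unaffected in the second year of life, although never seen at that age.

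The start-of-interval denominator removes most of this but not all. A child who leaves partway through an interval without an episode stays in the denominator as unaffected for the whole of it. In both cases the error is downward when withdrawal is unrelated to risk, and it grows with drop-out. The affected rows are part of the burden description for a co-primary objective and are broken down by country.

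**Working it through.** **The plan's own figures.** 1920 / (1 - 0.20) = 2400 enrolled, and 320 / 0.80 = 400 per country or region. Both match protocol 9.3 and 5.1. The documents give no expected value for proportion affected.

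**Inputs.** Drop-out d = 20% by 24 months (protocol 9.3). Event rate h = 8 x 20/1000 = 0.16 per child-year, from the protocol's illustrative hospitalization rate of 20 per 1000 and its statement that the LRTI rate will be eight times that.

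**Assumptions, not in the documents.** The event rate is constant, drop-out is exponential, and drop-out is unrelated to risk. The drop-out rate is then mu = -ln(0.80)/2 = 0.1116 per year.

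**Formulas**, for an interval starting at age a (years) with length L:

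- Risk with full follow-up: 1 - exp(-hL)
- Observed, start-of-interval denominator: [h/(h+mu)] x [1 - exp(-(h+mu)L)]
- Observed, at-birth denominator: the line above x exp(-mu x a)

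**12-23 months (a = 1, L = 1).** Full follow-up: 1 - exp(-0.16) = 14.8%. Start of interval: (0.16/0.2716) x (1 - exp(-0.2716)) = 14.0%. At birth: 14.0% x 0.894 = 12.5%. In counts, about 301 of the 2147 children still followed at 12 months would be seen with an episode: 301/2147 = 14.0%, but 301/2400 = 12.5%.

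| Age (months) | Full follow-up | Start of interval | At birth |
|---|---|---|---|
| 6-11 | 7.7% | 7.5% (-3%) | 7.1% (-8%) |
| 0-11 | 14.8% | 14.0% (-5%) | same |
| 12-23 | 14.8% | 14.0% (-5%) | 12.5% (-15%) |
| 0-23 | 27.4% | 24.7% (-10%) | same |

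Brackets show relative error. The two denominators coincide for intervals that start at birth.

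**Sensitivity to the event rate.** For h from 0.02 to 0.40 per year at 20% drop-out, the relative errors hardly move. At birth they are about -8% (6-11 months) and -15% (12-23 months). With start of interval they are about -3% (6-month intervals), -5% (12-month) and -9% to -10% (0-23 months).

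**Sensitivity to drop-out, at h = 0.16:**

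| Drop-out | 12-23 months, at birth | 0-23 months |
|---|---|---|
| 5% | -3.7% | -2.4% |
| 10% | -7.5% | -4.8% |
| 20% | -15.2% | -9.8% |
| 30% | -23.2% | -15.1% |

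**Second drop-out pattern.** Take a straight-line loss of 20% over 24 months and an illustrative true 12-23 month proportion of 10.0%. The proportion still followed falls from 0.90 to 0.80 across the second year, averaging about 0.85. The at-birth figure is therefore 8.5%, and the start-of-interval figure is 8.5/0.90, or about 9.45%. The relative errors agree with the first model.

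**The case against.** The strongest reply is that the governing text is clear enough. SAP 11.1.3 and the footnotes of the two co-primary templates agree on start of interval, and only a column label differs. Because the per-protocol set follows children up to their censoring, the natural reading of that denominator is children still being followed. On that reading the 12-23 month error is about half a percentage point on 10%. That is small beside the sampling error: with 36 events among 360 children (a 400-child region after 10% loss in year one), the exact Poisson interval is 7.0% to 13.8%. The analyses are descriptive, and the objective is also reported as person-time rates by the same intervals and countries.

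Most of this stands, and it limits the point. It does not remove the contradiction. The headings are what the output tables will print, 11.1.3 never says under follow-up, and Template 35 is consistently at birth.

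Four stronger readings that a reader might infer are not supported:

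- **That the co-primary figure is defined on children at birth.** The method text and the footnotes of Templates 9 and 10 say otherwise. Heading and footnote both say at birth only in Template 35, which covers exploratory definitions under a tertiary objective.
- **That the co-primary objective has no measure that allows for withdrawal.** SAP 11.1.1 stops person-time at last contact, and Template 13 gives Kaplan-Meier estimates at 6, 12 and 24 months. What is missing is a censoring-adjusted proportion specific to 6-11 or 12-23 months.
- **That country comparisons will be distorted by retention.** This could happen if drop-out differs by country, but the documents give no country-level drop-out figures.
- **That a difference between the 0-23 month row of Template 9 and the 24-month row of Template 13 would be an error.** A crude proportion and a cumulative probability are different summaries and need only be labelled as such.

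**Conclusion.** The point holds as an inconsistency that needs correcting before tables are produced. Following the headings, or Template 35 as written, would understate the 6-11 month rows by about 8% relative and the 12-23 month rows by about 15%. Following 11.1.3, with its denominator read as children still followed, leaves about 3%, 5% and 10% for 6-month, 12-month and 0-23 month intervals. That remainder is a property of any crude proportion under withdrawal and calls for a label rather than a new method.

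These sizes rest on 20% drop-out over 24 months, which is a planning allowance and not an observed figure, on its even or exponential timing, and on its being unrelated to RSV risk. They depend little on the event rate and strongly on actual drop-out.

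**What to change.** 1. In SAP 11.1.3, define the denominator as children still under follow-up at the start of the age interval.
2. Change the column headings of Templates 9, 10 and 35, and the footnote of Template 35, to match.
3. Label the figure as a crude observed proportion and add a column for the number censored within each interval.

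Optionally, add 1 minus a Kaplan-Meier estimate started at the beginning of each interval, among children then under follow-up and censored as in 11.1.1. This is a refinement and not a necessary correction.

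Items 1 to 3 cost SAP wording, template edits and one extra count. The optional estimate needs a little more programming, although Kaplan-Meier is already planned for the same six endpoints, and gives slightly wider intervals than the raw fraction.

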11.1.4. Computation of incidence proportion

Incidence proportion will be computed as the number of subjects had first episode in the age interval divided by the number of subject at risk of event at the beginning of the age interval. A subject that has an event will no longer consider of at risk, i.e. subjects with event in 0 - 1 month are excluded from denominator for future monthly incidence calculation. A 95% CI will be computed using an exact method.

11.1.5. Cox regression models

Cox regression models will be performed for the univariate analyses in order to obtain unadjusted hazards ratios of the determinants of interest.

200150 (EPI-RSV-005 BOD)

Statistical Analysis Plan Amendment 1 Final

In addition, a multivariable Cox regression model will be performed in order to estimate the relative contribution of each potential risk factor adjusting for the simultaneous effects of the other covariates. The model will include: time-independent covariates (e.g., country, gender etc.) and time-dependent covariates, breast feeding. Covariates selection will be done using statistical significance. Potential risk factors will be included in the multivariable models if univariate p-value will be less than 0.1.

The Table 15 details the time dependent status of the potential risk factors:

Table 15Time dependent status of the covariates

Potential risk factor	Time-dependent
Country of birth	No
Gender	No
Birth period	No
Gestational age at birth	No
Birth weight	No
Apgar at 5 mins of age	No
First degree relative with family history of asthma	No
Quartiles of cord blood maternal antibodies for RSV A	No
Quartiles of cord blood maternal antibodies for RSV B	No
Highest education level of the mother	No
Highest education level of the father	No
Number of people living in the household at month 3	No
Number of other children (<18 years old) living in the household at month 3	No
Subject in regular close contact with toddlers at month 3	No
The child live in a surrounding where people smoke daily at month 3	No
Breast feeding	Yes

Results from the multivariable Cox model will include hazards ratios (with 95% CI).

The number of covariates included in the model will depend on the number of events (at least 10 events per covariates).

Please note that the multivariable model will be performed only if the number of events is sufficient (at least 10 events per covariates). In addition, depending on the data other models could be explored or the model could be simplified.

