6.1.4.5. Time of birth relative to the transmission season

The transmission season period is defined:

- from April to September in the North hemisphere
- from October to March in the South hemisphere
- all year long in the tropical hemisphere

A summary of transmission season is displayed in the following table.

200150 (EPI-RSV-005 BOD)

				,
Statistical	Analysis	Plan	Amendment	1 Final

Country	Hemisphere	Transmission season period
Canada	North hemisphere	April 1 to September 30
United States	North hemisphere	April 1 to September 30
Finland	North hemisphere	April 1 to September 30
Argentina	South hemisphere	October 1 to March 31
South Africa	South hemisphere	October 1 to March 31
Thailand	Tropical hemisphere	All year long
Bangladesh	Tropical hemisphere	All year long
Honduras	Tropical hemisphere	All year long

Table 10Summary of transmission season by country

All subjects from tropical hemisphere will be considered to be born within the season.

Subjects from North hemisphere will be considered to be born within the season if they are born between April and September. Subjects from South hemisphere will be considered to be born within the season if they are born between October to March.

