6.6.3. Analysis of tertiary objectives: potential risk factors for RSV disease

For this objective, the analysis will be based on PPS.

The incidence, overall and by country, of first events of RSV-LRTI, RSV severe LRTI, RSV non severe LRTI (WHO definition) will be analysed using a Cox regression.

The following risk factors will be considered in the model:

- General:
 - Country of birth
 - Gender (as recorded in demography of extension phase)
 - Time of birth relative to the transmission season (see section 6.1.4.5)
- Characteristics at birth:
 - Gestational age at birth (see details section 6.1.4.1)
 - Birth weight (see details section 6.1.4.2)
 - Apgar at 5 mins of age (see details section 6.1.4.3)
 - Caesarian section
- Family history:
 - First degree relative with family history of asthma (see details section 6.1.4.4)
- Living environment and household composition:
 - Highest education level of the mother (see details section 6.1.4.6)
 - Highest education level of the father (see details section 6.1.4.6)
 - Number of people living in the household at month 3 (see details section 6.1.4.7)
200150 (EPI-RSV-005 BOD)

- Statistical Analysis Plan Amendment 1 Final
- Number of other children (<18 years old) living in the household at month 3 (see detail section 6.1.4.8)
- Subject in regular close contact with toddlers at month 3
- The child live in a surrounding where people smoke daily at month 3
- Breast feeding *

* Time dependent covariate; status is yes of subject ever breastfed from DOB until the end of breastfeeding given in the surveillance visit. Last day of month will be imputed for any partial date of breastfeeding end date.

As described in the section 11.1.5, covariates with univariate p-value less than 0.1 will be included in the multivariable model. The number of covariates included in the model will depend on the number of events (at least 10 events per covariates).

Please note that the multivariable model will be performed only if the number of events is sufficient (at least 10 events per covariates). In addition, depending on the data, other models could be explored or the model could be simplified.

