9. CHANGES FROM PLANNED ANALYSES

- Due to the number of subjects with examination visit but without surveillance visit:
 - RSV LRTI endpoints computed using data from examination visit were added to the endpoint RSV-associated RTI with a suspicion of involvement of the lower respiratory tract definition computed using data from surveillance visit
 - The delay between LRTI identification and swab sample is not considered in the case definition
 - The subgroup analysis by collection time of swabs (72 hours/48 hours from the start date of the case (date of the call), 72 hours/48 hours from the reported onset of symptoms) has been removed
- In protocol it is suggested to analyse by country and then pool by hemisphere and region. Pooling across such diverse settings is not developing strong messages about RSV incidence and therefore we limit our subgroup analysis to by country. Where the protocol described overall incidence we have preferred to only do pooled incidence across countries by year of life. This aids meaningful interpretation and minimises tables.
- In the analysis of the key healthcare utilization and health outcomes: the hospitalization status, intensive care unit attendance, clinical diagnosis of bronchiolitis or pneumonia, death has been replaced by: outpatient visit, emergency Room visit, inpatient Admission (non intensive care), innpatient Admission (intensive care), no consultation other than site clinic and other.
- In the analysis of the performance of case definition, the key health outcome does not include intensive care unit attendance, clinical diagnosis of bronchiolitis or pneumonia and death. Instead, hospitalization status according to WHO, GSK, Nokes, and exploratory case definition will be used for the analysis.
- The incidence rates of RSV-associated LRTI/severe LRTI as classified by the GSK and Nokes case definition are not computed.
- Incidence rate of all cause RTI provided instead of per protocol non-RSV associated RTIs as RSV RTIs are subset of all cause RTI. Hence analysis of all cause RTIs is more relevant and conventional in epidemiological studies.
- Descriptive statistics of the different types of healthcare utilization will not be provided among non-RSV-associated RTI with a suspicion of involvement of the lower respiratory tract, overall and by subgroups.

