												. 4	.00130		1-130	v-(100 DC)))
									Stat	isti	cal An	aly	sis Pla	n A	\mend	me	nt 1 Fi	nal
	Total		AR		BD		CA		FI		HN		SA		TH		US	
	N =		N =		N =		N =		N =		N =		N =		N =		N =	
	Value	%	Value	%	Value	%	Value	%	Value	%								
	orn		orn		orn		orn		or n		or n		orn		orn	1	orn	
Maximum																		
Missing																		
Subiect in																		
regular close																		
contact with																		
toddlers at																		
Month 3																		
Yes																		
No																		
Missing																		
The child live																		
in a																		
surrounding																		
where people																		
smoke daily at																		
Month 3																		
Yes																		
No																		
Missing						1		1										

N = total number of subjects

n/% = number / percentage of subjects in a given category

Value = value of the considered parameter

SD = standard deviation

AR = Argentina

BD = Bangladesh

CA = Canada

FI = Finland

HN = Honduras

SA = South Africa

TH = Thailand

US = US

Transmission season:

October to March for Argentina, South Africa;

April 2014 to September 2014 for Canada, Finland, United states;

All year long for Bangladesh, Honduras, Thailand

Note:

Gender information reported herein was collected during the ongoing extension study, causing some missing data Breastfeeding duration was provided for subjects who breastfed

200150 (EPI-RSV-005 BOD)

Statistical Analysis Plan Amendment 1 Final

Template 5 Summary of demographic characteristics of subjects with blood sample – overall and by time point (PPS sub cohort)

	Mont N =	h 2	Month N =	า 4	Month N =	6	Month N =	12	Month N =	18	Month N =	24
	n	%	n	%	n	%	n	%	n	%	n	%
Country												
Argentina												
Bangladesh												
Canada												
Finland												
Honduras												
South Africa												
Thailand												
US												
Gender of new born												
Male												
Female												
Missing												
Gestational age at birth (weeks)												
≤ 28												
29-32												
33-36												
≥ 37												

N = total number of subjects at each timepoint

n/% = number / percentage of subjects in a given category

Value = value of the considered parameter

Note:

Gender information reported herein was collected during the ongoing extension study, causing some missing data

Template 6 Number of subjects by center (Total enrolled cohort)

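### Coding every tropical child as born in season makes the unadjusted birth-season hazard ratio, and the p<0.1 screen built on it, a mixture of season and tropical-versus-non-tropical RSV risk

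*SAP*

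**What the plan says.** SAP section 6.1.4.5 defines the yes/no birth-season covariate. For the tropical countries, "All subjects from tropical hemisphere will be considered to be born within the season". The footnote to Template 4 (SAP 12.2.1) gives their season as "All year long for Bangladesh, Honduras, Thailand". In the other five countries the variable does vary with birth date; for example, "Subjects from North hemisphere will be considered to be born within the season if they are born between April and September".

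Birth season is a listed risk factor in SAP 6.6.3 (a tertiary objective) and a possible covariate in SAP 6.9.1 (the cord-blood antibody models, a secondary objective). Section 11.1.5 sets the method: "Cox regression models will be performed for the univariate analyses in order to obtain unadjusted hazards ratios of the determinants of interest". It then sets the entry rule: "Potential risk factors will be included in the multivariable models if univariate p-value will be less than 0.1". Section 6.9.1 applies the same rule. Template 17 and Templates 43 to 45 give birth season one row with two levels, in a layout where country is another row.

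On country, section 11.1.5 says "The model will include: time-independent covariates (e.g., country, gender etc.) and time-dependent covariates, breast feeding", but follows this with selection of covariates by statistical significance. Nothing in the SAP stratifies the birth-season term by country, restricts it to countries where it varies, or gives the tropical children their own level.

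**The concern.** In three of the eight countries the covariate is a constant. Those children can only add to the in-season group, and they bring their countries' RSV rates with them. The protocol's background section says that RSV incidence varies between countries and regions. A pooled, unadjusted birth-season hazard ratio then reflects two things at once: being born in season rather than out of it, and living in a tropical rather than a non-tropical country.

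Two uses are affected. Template 17 reports this hazard ratio and p-value as a risk-factor result. The same p-value decides whether birth season is adjusted for at all, both in the risk-factor models and in the cord-blood models. The error can go either way: a season effect that does not exist, or a real one cancelled and dropped.

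**Working it through.** **Nearest figure in the plan.** The documents give no birth-season hazard ratio. The only related figure is the design effect in protocol section 9.3: 1 + (160 - 1) × 0.02 = 4.18, which reproduces. It shows that the plan expects rates to vary between clusters.

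**Inputs from the documents.** Three of eight countries are tropical and all their children are coded in season. The screen is p<0.1, taken as two-sided, so |z| > 1.645. The enrolment target is 2400.

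**Assumptions, because the documents are silent.** 2400 / 8 = 300 children per country; half of non-tropical births in season; about 300 first events; no true season effect; tropical/non-tropical rate ratio R between 0.5 and 2.

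**Groups.** Tropical: 3 × 300 = 900, all in season. Non-tropical: 5 × 300 = 1500, with 750 in season and 750 outside. In season in total: 1650 of 2400 = 0.6875. Tropical share of the in-season group: 900 / 1650 = 54.5%.

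**Formulas.** Expected HR ≈ (900 × R + 750) / 1650. z = ln(HR) × √(300 × 0.6875 × 0.3125) = ln(HR) × 8.03.

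**Simulation check.** 2000 runs per scenario, 1920 / 8 = 240 children per country, two years of follow-up, 20% dropout, about 210 to 340 events, score test at p<0.1.

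| R | Expected HR | z | Passes screen, unstratified | Passes screen, stratified by country |
|---|---|---|---|---|
| 0.5 | 0.73 | -2.6 | 73% | 10% |
| 0.67 | 0.82 | -1.6 | 40% | 9% |
| 0.75 | 0.86 | -1.2 | not run | not run |
| 0.8 | 0.89 | -0.9 | 22% | 10% |
| 1 | 1.00 | 0 | 10% | 10% |
| 1.25 | 1.14 | 1.0 | 25% | 10% |
| 1.5 | 1.27 | 1.9 | 56% | 10% |
| 2 | 1.55 | 3.5 | 96% | 10% |

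The nominal pass rate is 10%. Simulated median hazard ratios were 0.71, 1.25 and 1.48 at R = 0.5, 1.5 and 2, so the formula is a close approximation.

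**Sensitivity.** At R = 1.5 the expected HR is 1.24 to 1.32 as the non-tropical in-season share goes from 2/3 to 1/3, and 1.20 to 1.33 as the tropical share of children goes from 25% to 50%. With only about 60 to 80 events, 20% (R = 0.67) and 25% (R = 1.5) of runs pass.

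**The opposite error.** Take a true within-country HR of 1.5, so that the non-tropical mean rate is (1 + 1.5) / 2 = 1.25 times the out-of-season rate, and tropical rates half that mean. The unadjusted HR is (3 × 0.5 × 1.25 + 2.5 × 1.5) / 5.5 = 1.02. In simulation of this case birth season passed the screen in 10% of runs unstratified and 87% stratified.

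**The case against.** **The adjusted model deals with it.** Section 11.1.5 plans a multivariable model and names country first among its covariates. When tropical and non-tropical rates differ enough to distort the season row, country will usually pass the screen too: in the simulations with no true season effect, season passed while country failed in 0% to 13% of runs. This largely stands for the adjusted hazard ratio. It does not repair the unadjusted hazard ratio that is reported, nor bring back a season effect already screened out. Country also remains subject to selection. Eight countries need seven terms, or 70 events if the limit of ten events per covariate is counted per term, and the SAP allows the model to be simplified.

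**A by-country Cox analysis is mentioned.** Section 6.6.3 refers to incidence overall and by country in its Cox sentence. By-country models would be free of the problem, although the term cannot be estimated in the tropical countries. Template 17 shows only a pooled layout, so the intention needs to be stated.

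**The size is assumed.** This stands. The closest statement, in protocol section 9.3, is that hospitalization rates in industrialized and developing countries are similar, which would point towards R near 1. It concerns hospitalization only, and developing is not the same as tropical.

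**The stakes are limited.** Template 17 serves a tertiary objective, SAP section 7 calls the analyses descriptive, and in Templates 43 to 45 birth season is only an adjustment variable. That limits the weight of the point, but a descriptive hazard ratio should still describe the factor it is labelled with, and here a p-value drives selection.

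**Stronger readings that the documents do not support.** A reader might infer that the birth-season hazard ratio is merely a comparison of countries. It is not: five countries supply a genuine within-country contrast. A reader might also take "Pooling across such diverse settings is not developing strong messages about RSV incidence" in SAP section 9 as an admission that no pooled model is valid. That sentence concerns incidence subgroups, and the SAP goes on to keep incidence pooled across countries by year of life; it does not address the Cox models.

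**Conclusion.** The point holds as a mixture of two contrasts. The mechanism follows from the coding rule and the absence of any stratification, and does not depend on which calendar months define the season. Whether it causes bias depends on R: none at R = 1, modest and often below the screening threshold when R is near 1 (z = -1.2 at R = 0.75), and large enough to pass the screen in most runs at R = 0.5, 1.5 or 2 with roughly 200 to 340 events. These sizes rest on equal country numbers, an even split of non-tropical births and assumed event counts. The documents do not show that tropical and non-tropical rates in this cohort differ, so they do not show that the reported figure will be wrong; they show only that it cannot be read as a birth-season effect without assuming equal rates. An adjusted hazard ratio from a model that contains country is not affected by this mixture.

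**What to change.** In SAP 11.1.5, with matching text in 6.6.3 and 6.9.1, state two things. First, the birth-season term is estimated with the baseline hazard stratified by country, both for its reported univariate hazard ratio and for its p<0.1 screen. Second, country is kept, as a stratum or a covariate, in any multivariable model that contains birth season. Footnote Templates 17 and 43 to 45 to say that the tropical countries do not contribute to this row.

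Keep the tropical children in the models for every other covariate. Recoding them as not applicable is unnecessary once the term is stratified, and in a complete-case multivariable model it could remove three countries.

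The cost is a few lines of SAP text and a strata option in the program. The birth-season row is then informed only by the five seasonal countries, five-eighths of the children if countries are equal in size, so its confidence interval may be wider. The tropical children carry no within-country information on this factor, so no valid evidence on it is lost.
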